In line with new guidelines from the American College of Sports Medicine (ACSM), we will exclude participants if they have any known cardiovascular, pulmonary, or renal disease. Those who do not have any signs or symptoms, nor diagnosis, will not require medical clearance. This is also in line with new regulations from ACSM based on studies finding low predictability of adverse event by CVD risk factors, coupled with high prevalence in older adults. Only those older adults interested in participating in the research study that have any signs or symptoms of cardiovascular, pulmonary, or renal disease or mild musculoskeletal issues (such as osteopenia, osteoporosis, or arthritis) will be required to submit a medical clearance form signed by his or her physician before participating in exercise testing or training (FitRec Personal Training Medical Waiver form). In addition, we will exclude participants if they have any contraindicator of MR imaging (e.g. non-removable ferromagnetic metal in or on the body), bioelectrical impedance analysis (BIA; e.g. pacemaker), or if they have any neurological or psychiatric conditions or disorders that are known to affect the brain and cognitive functions. In addition, participants will be excluded if they are physically active, or are not considered "sedentary": The American College of Sports Medicine defines a sedentary lifestyle as a lifestyle in which a person is not participating in at least 30 minutes of moderate intensity physical activity on at least three days per week for at least three months (definition according to American College of Sports Medicine, Thompson et al., 2010). Finally, individuals will be excluded if they self-report susceptibility to severe motion sickness or claustrophobia, given that (1) the cognitive task performed in the MRI scanner may cause discomfort for individuals who are susceptible to motion sickness, and (2) being inside the MRI scanner may cause discomfort for individuals who are susceptible to claustrophobia.

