and compare them between and within groups with mixed-design ANOVAs. We will use baseline fitness as a covariate. Because the entorhinal cortex and the hippocampus are our primary brain regions of interest, we will use a seed-based functional connectivity approach. We will compare task-related functional connectivity: 1) pre versus post intervention, and 2) aerobic exercise versus control. We will use the psycho-physiological interaction (PPI) approach91 using the Generalized PPI Toolbox92 for SPM8. The time course from a seed region constitutes the physiological variable, and the contrast of interest (e.g. high memory load > low memory load) constitutes the psychological variable in the PPI model. Our search space will be restricted to the medial temporal lobe region. We will determine the PPI variable by calculating the voxel-wise product between the physiological and the psychological variables. We will also correlate SPMs and functional connectivity strength with cognitive test scores. Analyses will include nuisance regressors (e.g. head motion).

Specific Aim #2:

Data Analysis. See Aim #1. The behavioral outcome variables of the primary cognitive task (allocentric navigation task) are distance traveled and movement speed. Addicional outcome variables are neuropsychological test scores and spatial reasoning test scores. Analyses will be as described for Specific Aim #1. In addition, we will compare two groups that differ in relative EC volume or path integration ability (by median split) using descriptive statistics (means, confidence intervals) due to the exploratory nature/ small sample size.

Sample Size

Sample Size Justification

Approximately 94 participants will be recruited total for the study: For the exercise training program

/study intervention, approximately 84 participants will be recruited with the aim to enroll 42 participants, 21 per group; for the cognitive and fMRI pilot studies, an additional 10 participants will be recruited with the aim to enroll 5 participants in the cognitive pilot and 5 participants in the fMRI pilot. Thus, this totals 94 participants (84 + 5 + 5 = 94) required to complete the cognitive pilot, fMRI pilot, and exercise training program/study intervention.

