Walking and moderate-intensity physical activities are associated with a very low risk of musculoskeletal complications, but jogging and running are associated with increased risk of injury to the muscles, bones or joints. Acute heart attacks and sudden cardiac death can be triggered by unaccustomed vigorous physical exertion, particularly in sedentary men and women who have signs or symptoms of heart disease.

MRI risks

The MRI uses a strong magnet. The magnet may affect pacemakers, artificial limbs, and other medical devices that contain iron. The magnet will stop a watch that is close to the magnet. Any loose metal object has the risk of causing damage or injury if it is pulled toward the strong magnet. The loud acoustic noise from the MRI machine may cause hearing damage. Participants may also experience claustrophobia (fear of small spaces) or anxiety while in the magnet, because the top and sides of the machine will be very close to the body. There is a chance that the person performing the MRI may notice an incidental finding. It is possible that participants will be unnecessarily worried about the incidental findings.

Risks of completing tasks

Participants may get tired during the cognitive tasks.

Questionnaire risks

Participants may feel emotional or upset when answering some of the questions.

Loss of confidentiality

The main risk of using and storing identifiable information for research is a potential loss of confidentiality.

How risks will be

Risks associated with the cardiovascular fitness and strength tests

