Because it is very strenuous to reach maximum oxygen uptake even after rest, and thus, may pose a health risk for some participants, we will estimate, rather than measure, the level of maximum oxygen uptake. Therefore, participants will perform a submaximal, incremental fitness test. This test will follow established standards of the American College of Sports Medicine (ACSM). We will instruct participants to let the technician know about any discomfort, such as dizziness, nausea, extreme shortness of breath, and extreme leg fatigue. Participants may ask to stop the test at any time. The staff members who will perform the fitness testing have current certification in cardiopulmonary resuscitation (CPR). We will ask participants not to engage in strenuous physical activity for 24 hours prior to the test. Participants are advised not to participate in the fitness assessment if they have any heart or lung conditions or symptoms, or if they have any physical impairment that would preclude them from performing the test safely. We will screen them for these conditions and symptoms prior to testing. During the tests we will monitor heart rate, blood pressure and perceived exertion. Only well-trained personnel (technicians, physiologists, nurses or physicians) will conduct the exercise test.

To reduce the risks associated with strength testing, participants will perform wrap-up exercises, and trained individuals will instruct them in proper technique. Participants will be able to take breaks as

Risks associated with bioelectrical impedance analysis (BIA)

We will exclude participants with pacemakers and defibrillators from participating in this study.

Risks associated with exercise

To reduce the risk of musculoskeletal injury and complications associated with exercise, the exercise training program will be tailored to each participant's ability level and supervised by an experienced

trainer. The trainer will instruct each participant in proper technique. To reduce injury risk, each exercise session will include a light cardiovascular warm-up, cool-down and stretching, and the amount and intensity of the exercise will gradually increase over the 12 weeks of the exercise training program.

MRI risks

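### People with heart or lung symptoms but no known disease may take the fitness test with a signed clearance under the screening rules, yet the risk section advises them not to take it

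*Combined protocol and SAP*

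**What the plan says.** All references are to the combined protocol and SAP.

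**Study Visit 1, Screening, part I.** On diagnosed disease the text is categorical: "we will exclude participants if they have any known cardiovascular, pulmonary, or renal disease". A separate rule covers interested older adults "that have any signs or symptoms of cardiovascular, pulmonary, or renal disease or mild musculoskeletal issues". They are not excluded; each "will be required to submit a medical clearance form signed by his or her physician before participating in exercise testing or training". A little further on, a positive answer in the exercise-readiness sections of the general screening form, or on the health history questionnaire, prompts the principal investigator to consult a collaborator. The principal investigator is also to ensure that the fitness and strength testing suits each participant.

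**How risks will be minimised, cardiovascular fitness and strength tests.** Here the wording is: "Participants are advised not to participate in the fitness assessment if they have any heart or lung conditions or symptoms". Shortly after comes: "We will screen them for these conditions and symptoms prior to testing". The section does not mention the clearance form and does not say what follows from a positive screen.

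**Study Visit 40.** The follow-up fitness visit uses the same procedures as Study Visit 2, which contains the submaximal treadmill test from which VO2max is estimated.

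**The concern.** Take a sedentary older adult with cardiac or respiratory symptoms, no diagnosis and a signed clearance. The screening section opens the treadmill test to this person; the risk section advises the person against it. Staff cannot follow both.

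Two things are at stake. The first is a safety instruction. The section on exercise risks itself says that unaccustomed vigorous exertion can trigger cardiac events, "particularly in sedentary men and women who have signs or symptoms of heart disease". The second is the trial population: whether such a person is tested and enrolled, or leaves before training, depends on which section is treated as governing. The same uncertainty returns at follow-up, where it can affect an outcome measurement after randomisation.

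**Working it through.** No sample size, power or error-rate figure is involved, so the check is a comparison of the texts.

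**Step 1: who is affected.**

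| Person | Screening, part I | Risk-minimisation section | Consistent? |
|---|---|---|---|
| Known heart or lung disease | Excluded | Advised against the fitness assessment | Yes, in direction |
| Heart or lung symptoms, no diagnosis, signed clearance | May be tested and trained | Advised against the fitness assessment | No |
| Renal symptoms or mild musculoskeletal problems, signed clearance | May be tested and trained | Not named, apart from physical impairment that makes the test unsafe | No direct conflict |
| No symptoms and no diagnosis | No clearance needed | Not addressed | Yes |

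The conflict is confined to the second row.

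**Step 2: does the risk section carry an implied exception?** Its advice on physical impairment is limited to impairments that would prevent safe performance of the test. Its advice on heart and lung symptoms has no such limit and no reference to clearance. An exception cannot be read out of the sentence.

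**Step 3: does another section settle it?** The consultation step in screening creates a review but gives no decision rule for a symptomatic person with clearance. The list of instruments includes the clearance form only where applicable. Neither says that clearance overrides the advice, or the reverse.

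**Step 4: consequence at baseline.** The Study Summary starts training after the three initial visits. The Exercise Training section bases aerobic intensity on the Study Visit 2 cardio-respiratory results and the control programme on the Study Visit 2 session. It also indicates that anticipating a missed study visit, with Visit 2 among those listed, can lead to exclusion. Taken together, these imply that a person who declines the baseline test would not go on to training. The baseline effect is on who enters the trial.

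**Step 5: consequence at follow-up.** The risk section's advice is not tied to one visit, and Visit 40 repeats Visit 2. A participant who develops symptoms during the 12 weeks falls under the advice at Visit 40. The rule on anticipated missed visits does not help, because new symptoms are not anticipated. If the participant follows the advice, the follow-up VO2max is missing. VO2max is a secondary outcome, and its planned analysis is a repeated-measures ANOVA of group by time (pre, post), which needs both values. The Data Analysis section does not say how a missing value is handled.

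**Step 6: size.** The documents give neither the number of symptomatic people expected at entry nor the number expected to develop symptoms. Neither consequence can be quantified.

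**The case against.** The strongest reply is that the risk section gives advice, not an eligibility rule. Its statement that participants will be screened points back to the Study Visit 1 procedures, so a general caution and a specific clearance rule could be read together, with the clearance rule operative. It stands that a cleared person could still be tested and that nothing forbids it. It does not stand that the text says so: the advice covers any symptoms, and a reader has to supply the exception.

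Second, positive screens are reviewed individually by the principal investigator with a collaborator. That is a real safeguard and means such a person is not without a decision process. It does not tell the decision-makers which section to apply.

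Third, the re-screening section cites a numbered eligibility list, and the screening section refers to attached forms; none of these is in the text available. They may say how cleared symptomatic people are handled. That limits confidence, but the two sections would still need to agree.

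Fourth, the statement on exercise risks concerns vigorous exertion and heart disease. It does not mention lung symptoms or a submaximal walking test, so it supports the safety concern only in part.

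A reader might also infer a loss of baseline data. The fMRI analysis plan says "We will use baseline fitness as a covariate", so each enrolled participant without a baseline test would be missing from those models, at 1/42 = 2.4% of the planned 42. The documents do not support this. It needs a person who skips Visit 2, trains and is scanned anyway, and the sequence in step 4 of the working points the other way. The 2.4% is only the share that one person makes up of 42, with no stated count behind it. A person who declines the baseline test would most likely be lost between the approximately 84 recruited and the 42 enrolled.

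**Conclusion.** The contradiction is real but narrow. It concerns heart or lung symptoms without known disease, in people who hold a signed clearance. Its weight comes from its being a safety instruction that also bears on entry to the trial, with a secondary risk of missing follow-up VO2max values. It should be corrected, but it does not undermine the primary comparisons.

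Confidence is medium. The conclusion assumes that the unseen eligibility list and forms do not already resolve the conflict. The follow-up consequence further assumes that some participants develop symptoms during training and act on the advice; the documents allow this but give no frequency.

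**What to change.** Reconcile the Study Visit 1 screening text with the risk-minimisation section, so that a single rule states what happens to a person with heart or lung symptoms, no known disease and a signed clearance. State that rule identically in both sections and in the matching participant-facing wording. Make explicit that it applies at Study Visit 2 and at Study Visit 40, including to symptoms that first appear during training. Which rule to adopt is for the clinical team; this review takes no position.

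The cost is a short protocol amendment and a matching change to participant materials. Depending on the rule chosen, slightly fewer people may be eligible. No planned analysis or sample-size calculation has to change.
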